### 13.5.1.3 Graph Presentation

The proportion of responders from the model-based analyses will be displayed graphically over time with the y-axis representing the proportion meeting the responder definition and the x-axis the study Week 10, Week 14 and Week 18.

### 13.5.1.4 Supportive Analyses: Proportional Odds Analysis

In addition to serial evaluation of A4 response defined as A4  $\leq$  1x, 1.25, 1.5x, 1.75x and 2x ULN, a combined A4 ordinal response will be analyzed, again via a GEE approach. Study Week

18 A4 response will be categorized for each subject as  $\{A=[\leq 1x]; B=[>1x \text{ to } \leq 1.25x]; C=[>1.25x \text{ to } \leq 1.5x]; D=[>1.5 \text{ to } \leq 1.75x]; E=[>1.75 \text{ to } \leq 2.0x]; \text{ and } F=[>2x]\}$  ULN. If there are too few subjects ( $n < 5$ ) in any of the categorizations A to F, the categorized will be collapsed to  $\{\tilde{A}=[\leq 1x]; \tilde{B}=[>1x \text{ to } \leq 1.5x]; \tilde{C}=[>1.5x \text{ to } \leq 2.0x]; \text{ and } \tilde{D}=[>2x]\}$ .

The model will include ordinal A4 response (= A, B, C, D, E, F; or  $\tilde{A}$ ,  $\tilde{B}$ ,  $\tilde{C}$ ,  $\tilde{D}$  if categories are collapsed) as the dependent variable; treatment group (0 = placebo, 50 = 50 mg QD tildacerfont, 100 = 100 mg QD tildacerfont, and 200 = 200 mg QD tildacerfont), time (=study week 10, 14 and 18), sex (0=male, 1=female), and the interaction of treatment and time as categorical covariates; log baseline A4 and baseline GC dose (in HCe) as continuous covariates. The link function will be cumulative logit and distribution will be multinomial. Subject IDs are used to identify the repeated measures of visits within subjects with an exchangeable working correlation structure. If the model fails to converge, the following working correlation structures will be tried in order until convergence is reached: unstructured, independent and AR(1). The significance level will be 0.05 2-sided.

The cumulative odds ratio for response at study Week 18 to each tildacerfont dose level versus placebo group, together with the associated 95% CI and 2-sided p-value will be extracted from the model. The same will also be extracted for the cumulative odds ratio of response at 10 and 14 weeks. SAS code will be of the form,

```
PROC GENMOD DATA=x;
  CLASS SUBJECT TREATMENT VISIT;
  MODEL CATRESPONSE = TREATMENT VISIT TREATMENT*VISIT / DIST=MULTINOMIAL
    LINK=CLOGIT TYPE3 AGGREGATE=TREATMENT;
  REPEATED SUBJECT=PATIENT/TYPE=IND;
  LSMESTIMATE TREATMENT 'CUM OR 50MG V PCBO' -1 1 0 0 / EXP CL ALPHA=0.05;
  LSMESTIMATE TREATMENT 'CUM OR 100MG V PCBO' -1 0 1 0 / EXP CL ALPHA=0.05;
  LSMESTIMATE TREATMENT 'CUM OR 200MG V PCBO' -1 0 0 1 / EXP CL ALPHA=0.05;
  RUN;
```

### **13.5.2 17-OHP Responder Analysis**

The Exploratory Efficacy Analysis 3.2 in [Table 1](#) is the proportion of classic CAH subjects who were randomized into the study who achieve adequate control of serum 17-OHP levels (defined as  $17\text{-OHP} \leq 1200 \text{ ng/dL}$ ) after 12 weeks of randomized, double-blinded treatment.

These data will be analyzed in the exact same manner as Exploratory Efficacy Analysis 3.1 with the only difference being the exclusion of  $\log A4$  as a covariate and the inclusion of the randomization stratification variable (study Week 4  $A4$  value [ $0 = A4 \leq 4 \times \text{ULN}$ ;  $1 = A4 > 4 \times \text{ULN}$ ]) as a fixed effect in the model.

### **13.5.3 TART Lesion Volume CFB at Week 18**

The Exploratory Efficacy Analysis 3.3 in [Table 1](#) is the CFB in TART lesion volume after 12 weeks of randomized, double-blinded treatment for those who had detectable TARTs at Baseline in the Male ITT population. The analysis will be constrained to only those subjects with evaluable baseline and post baseline ultrasound results. Missing data will not be imputed.

#### **13.5.3.1 Statistical Modeling and Testing**

Statistical analysis will be achieved via an ANCOVA model. If non-Normality is evidenced via Normal scores plot and plots of predicted versus residual values, the analysis will be accompanied by a rank-based ANCOVA model. The change from baseline to study Week 18 (12 weeks of randomized treatment) on the log scale will be the dependent variable; randomized treatment group ( $0 = \text{placebo}$ ,  $50 = 50 \text{ mg QD tildacerfont}$ ,  $100 = 100 \text{ mg QD tildacerfont}$ , and  $200 = 200 \text{ mg QD tildacerfont}$ ) as a fixed effect; baseline TART Volume and the baseline GC dose (in HCe) as continuous covariates; the randomization stratum ( $A4 \leq 4 \times \text{ULN}$  versus  $A4 > 4 \times \text{ULN}$ ) as categorical explanatory variables. The estimation method for the ANCOVA model will REML. A significance level of 0.05 2-sided will be applied.

The ranked value is obtained by ranking all non-missing change from baseline values at the specified analysis visit, if a rank-based model is used.

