To evaluate the effect of tildacerfont in reducing ATCH in subjects with classic CAH over 12 weeks	3.13.	Absolute change from baseline in ATCH as determined via application of the delta theorem to the log scale analysis results after 12 weeks on double-blind, placebo-controlled treatment (Week 18)
To evaluate the effect of tildacerfont in reducing ATCH in subjects with classic CAH over 12 weeks	3.14.	Change from baseline in ATCH as assessed on the log scale after 12 weeks on double-blind, placebo-controlled treatment (Week 18)

Objective	Efficacy Analysis	
To characterize dose-exposure of Tildacerfont in CAH	3.15.	Estimate the within subject correlation of A4 and 17-OHP log scale values with tildacerfont plasma concentrations over time
Exploratory Efficacy (Optional Open-Label Extension Period) - Outside the Scope of this SAP		
To evaluate the effect of tildacerfont in reducing GC use to near-physiologic levels in subjects with classic CAH	4.1.	Proportion of subjects with GC dose $\leq$ 25 mg/day in HCe and A4 $\leq$ ULN at end of treatment (EOT)
To evaluate the percentage change in GC use in subjects with classic CAH	4.2.	Percent change from baseline in GC dose at EOT
To evaluate the effect of tildacerfont in reducing cardiovascular risk in subjects with classic CAH and at least one cardiovascular risk factor at baseline	4.3.	Proportion of subjects with improvement in at least one cardiovascular risk factor at EOT
To evaluate the effect of tildacerfont in eliminating TART(s) in male classic CAH subjects with TART(s) at baseline	4.4.	Proportion of male subjects without TART(s) at EOT who had TART(s) at baseline
Safety		
To evaluate the safety of tildacerfont in subjects with classic CAH	5.1.	AEs, SAEs

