#### **9.3.13 Change from Baseline on the Log Scale**

The change from baseline on the log scale is calculated as the difference of the log (post-baseline assessment) subtracted by the log (baseline assessment). It is also mathematically equivalent to the log of the ratio of the post-baseline assessment divided by the baseline assessment.

$$\begin{aligned} \text{change from baseline on the log scale} &= \log(\text{post baseline assessment}) - \log(\text{baseline assessment}) \\ &= \log \left( \frac{\text{post baseline assessment}}{\text{baseline assessment}} \right) \end{aligned}$$

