#### **9.3.21 Testicular Adrenal Rest Tumor Volume**

For each TART assessment, the total number of TARTs will be captured as well as the size (lesion volume) of each TART individually. The total lesion volume of all detectable TARTs per subject will be calculated and will be compared against baseline total lesion volume.

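### A total TART volume of zero at Week 18 has no defined value in the log-change ANCOVA, and the SAP gives no rule for it

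*SAP*

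**What the plan says.** SAP 13.5.3.1 fits an ANCOVA to Week 18 TART volume: "The change from baseline to study Week 18 (12 weeks of randomized treatment) on the log scale will be the dependent variable". SAP 9.3.13 defines log-scale change as log(post) minus log(baseline) and adds no constant. SAP 9.3.21 defines the volume: "The total lesion volume of all detectable TARTs per subject will be calculated and will be compared against baseline total lesion volume".

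SAP 13.5.3 sets the analysis set and the missing-data rule: "The analysis will be constrained to only those subjects with evaluable baseline and post baseline ultrasound results. Missing data will not be imputed".

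If diagnostic plots suggest non-Normality, "the analysis will be accompanied by a rank-based ANCOVA model". On what is ranked, the SAP says: "The ranked value is obtained by ranking all non-missing change from baseline values".

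No section says what to do with a volume of zero. The half-limit substitution in SAP 10.2.3 covers laboratory values only. Protocol 9.4.4.1 specifies ANCOVA on change in lesion volume without a log transform, and SAP Section 15 does not list the transform among its changes.

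**The concern.** A man whose TARTs have all become undetectable by Week 18 meets the SAP 13.5.3 condition for inclusion, because both ultrasounds are evaluable. The model then has no value for him. He leaves the analysis because of his outcome, and on the log or percent scale that outcome is the most favourable one possible. If this happens more often on drug than on placebo, the estimated drug effect is too small and nothing in the log-model output shows it.

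The geometric means and geometric mean change planned in SAP 13.5.3.2 fail in the same way. The ANCOVA is also a small one. It is limited to men with a TART at baseline and estimates 7 mean parameters (1 intercept + 3 treatment + 1 stratum + 2 covariates), so each lost man matters.

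**Working it through.** The documents give no sample size, TART prevalence, volume SD or resolution rate for this analysis, so there is no stated figure to reproduce. The check has three steps.

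**1. Apply the SAP's definitions.** With Week 18 total volume V18 and baseline volume V0 > 0, the outcome is log(V18) − log(V0).
- If one lesion of several disappears, V18 > 0 and the outcome is finite.
- If no TART is detectable, the total is V18 = 0. Log(0) is undefined, SAS returns a missing value, and the record drops out of the model.
- Raw change is 0 − V0 and percent change is −100%. Both are defined, so the raw and percent-change descriptives in SAP 13.5.3.2 still include this man.

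**2. Possible size in one arm (assumed inputs).** Suppose the log ratio is Normal with geometric mean 0.70 and SD 0.5, and the lowest fraction p is recorded as zero and lost. The retained geometric mean ratio is 0.70 × exp{0.5 × φ(z_p)/(1 − p)}, where z_p is the p-quantile of the standard Normal and φ its density.

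| p lost | Retained ratio |
|---|---|
| 5% | 0.74 |
| 10% | 0.77 |
| 20% | 0.83 |
| 30% | 0.90 |

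These figures are for the arm that loses the men. The same loss on placebo would move the comparison the other way.

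**3. What the log model would show (assumed data, 6 men per arm).** Baseline volumes are 2.0, 1.5, 1.0, 0.8, 0.5 and 0.3. Week 18/baseline ratios on drug are 0.70, 0.80, 0.60, 0.75, 0.65 and 0.70. On placebo they are 1.05, 0.95, 1.00, 1.10, 0.90 and 1.00. The drug-arm men with the smallest lesions are then set to zero in turn.

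| Drug-arm men at zero | Retained on drug | Drug/placebo ratio, log model | Percent-change difference, zeros kept |
|---|---|---|---|
| 0 | 6 | 0.698 | −30.0 points |
| 1 | 5 | 0.698 | −41.7 points |
| 2 | 4 | 0.710 | −52.5 points |
| 3 | 3 | 0.697 | −65.0 points |

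The log-model ratio barely moves while up to half the drug arm resolves.

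Adding a constant c before taking logs does not settle the matter. With 1 of 6 men at zero, the ratio is 0.29 (c = 0.001), 0.42 (c = 0.01), 0.55 (c = 0.05) or 0.61 (c = 0.1).

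Ranking raw change keeps the resolved man but need not rank him best. His change is −0.3, behind −0.6 for the 2.0 lesion (2.0 × −0.30) and −0.4 for the 1.0 lesion (1.0 × −0.40). On percent change, −100% is always the lowest value.

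**The case against.** **The rank companion may already keep these men.** A reader might infer that it loses the same subjects. The SAP does not establish that. SAP 9.3.11 defines change from baseline, without qualification, as a raw difference, and 9.3.13 defines log-scale change separately. SAP 13.5.6.1 uses the same ranking sentence for SF-36, which is not logged. Read by those definitions, a resolved man has a non-missing raw change and is ranked. However, the only change that 13.5.3.1 names as dependent variable is the log change, so the text is open. The rank model also runs only if non-Normality is seen, and residuals exist only for retained men, so that check cannot detect the zeros.

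**Resolution by Week 18 may be rare.** A reader might take SAP Table 1 endpoint 4.4, "Proportion of male subjects without TART(s) at EOT who had TART(s) at baseline", to mean that the SAP expects it. That endpoint belongs to the open-label extension, is marked as outside this SAP, and concerns end of treatment after up to 240 further weeks. Protocol Section 3 words the matching endpoint as a reduction, not an absence. It shows only that resolution was thought possible. The trigger is also narrow, since the total must be zero. These points limit how often the problem would arise; they do not supply the missing rule.

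**Reporting and consequence are limited.** Resolved men remain in the raw and percent-change descriptives. The Week 76 TART analysis (SAP 13.5.7) follows the SF-36 ANCOVA, which is not logged. Protocol 9.4.3.2 and 9.6 still label Week 18 TART volume as secondary, but SAP Table 1 makes it exploratory, SAP 10.5 gives it no alpha control, and SAP Section 4 makes the SAP govern. All of this stands.

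**Conclusion.** The gap is real. Followed as written, the SAP includes a man with complete resolution in the analysis set and then gives the log ANCOVA no value for him. The SAP does not say that he is dropped. That follows from the undefined log, the bar on imputation and the lack of a zero rule.

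It would go too far to say that the analysis is biased toward no effect. That direction holds only if complete resolution is more frequent on drug, and the documents give no rates. The ratios of 0.74 to 0.90 rest on an assumed geometric mean of 0.70, a log SD of 0.5 and losses of 5% to 30% in one arm. They show scale and are not a forecast. The affected results are the Week 18 log ANCOVA and the geometric summaries of an exploratory endpoint, so the primary conclusion does not depend on this.

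**What to change.** Before unblinding, amend SAP 13.5.3 as follows:
- State that the rank-based ANCOVA will always be run and is the main TART analysis. Rank percent change (or, equivalently in order, the log ratio), and give every man with total volume zero the best, tied rank.
- Report the number of men with complete resolution by arm.
- If the log model is kept as supportive, substitute a pre-stated value for zero based on the ultrasound detection limit, with a sensitivity range, because the result depends strongly on that value.
- List the log transform in SAP Section 15 as a change from Protocol 9.4.4.1.

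The cost is a few sentences and no new data. The drawback is that a rank analysis gives a test and not a ratio estimate, so the size of effect would come from the descriptives, the resolved counts and the supportive log model.

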### **13.5.3.2 Reporting Results**

#### **Summary of Descriptive Statistics**

Descriptive statistics (11-point) for TART lesion volume, change from baseline in TART lesion volume, and % change from baseline will be presented by scheduled time point (i.e., Baseline and study Week 18). Geometric means and geometric mean change from baseline, along with the associated log scale SDs will also be presented.

#### **Presentation of Analysis Results**

The log scale change from baseline (CFB) least squares (LS) means will be extracted from the model for each tildacerfont dose and placebo, along with the associated SEs and 95% CIs. Further, the treatment effect for each tildacerfont dose versus placebo, being the corresponding difference in log scale LS means, will also be extracted along with the associated SE, 95% CI and 2-sided p-values.

To facilitate ease of interpretation, the log scale CFB LS means for each tildacerfont dose and placebo and the difference between each tildacerfont dose and placebo in log scale CFB LS means (along with the associated 95% CI) will be back transformed as described for the Primary Efficacy Analysis.

### **13.5.4 Correlation of Tildacerfont Plasma Concentration vs Dose**

Exploratory Efficacy Analysis 3.4 in [Table 1](#) is the correlation of tildacerfont plasma concentration versus dose. This will be explored by presentation of PK descriptive statistics by dose and scheduled time point (i.e., study Week 10 and 18). Geometric means and geometric mean change from baseline, along with the associated log scale SDs, will be presented.

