9.4.4.2 Correlation of Tildacerfont Plasma Concentration vs Dose

The correlation of tildacerfont plasma concentration versus dose will be explored by presentation of PK descriptive statistics by dose and scheduled time point (i.e., study Week 10 and 18).

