## 5.2 Study Treatment

### 5.2.1 Study Drug Administration

During the Run-in Period, subjects will take placebo for 6 weeks. In Part A of the study (the first 12 weeks of the Treatment Period), subjects will receive randomized study drug treatment (i.e., tildacerfont 50, 100, or 200 mg QD or matching placebo) without dose escalation. During Part B (the second 12 weeks of the Treatment Period) and Part C (the last 46 weeks of the Treatment Period), all subjects will receive tildacerfont and the dose level will be determined as follows.

- Subjects who were randomized to placebo in Part A will receive 100 mg tildacerfont QD at the beginning of Part B (Week 18).
- Subjects who were randomized to 200 mg tildacerfont QD in Part A will continue to receive tildacerfont at 200 mg QD throughout Parts B and C.
- Based on A4 results from the Week 18 and Week 24 visits, eligible subjects may undergo a tildacerfont dose escalation after each of these study visits. The RTSM system will assign appropriate dose levels of tildacerfont based on subjects' A4 results (i.e., A4  $\leq$  ULN or A4  $>$  ULN) at Weeks 18 and 24. Specifically:

- o Subjects taking tildacerfont 50 mg QD will either continue to receive the same dose (if A4  $\leq$  ULN) or be escalated to 100 mg tildacerfont QD (if A4  $>$  ULN and the subject is tolerating his/her current tildacerfont dose)
  - o Subjects taking 100 mg tildacerfont QD will either continue to receive the same dose (if A4  $\leq$  ULN) or be escalated to 200 mg tildacerfont QD (if A4  $>$  ULN and the subject is tolerating his/her current tildacerfont dose).
- At Week 30, all subjects will be escalated to 200 mg tildacerfont QD.

During the optional Open-Label Extension Period, subjects will continue to receive tildacerfont at 200 mg QD.

Tildacerfont is produced as a 50 mg tablet. The placebo is produced to look identical to the tildacerfont tablet. To maintain the blind, all subjects will receive the same number of study drug tablets, and take 4 tablets a day with the appropriate number of tildacerfont and/or placebo tablets for the assigned. The 200 mg tildacerfont dose will contain 4 tildacerfont tablets in each compartment; the 100 mg tildacerfont dose will contain 2 tildacerfont tablets and 2 placebo tablets; the 50 mg tildacerfont dose will contain 1 tildacerfont tablet and 3 placebo tablets; and the placebo dose will contain 4 placebo tablets.

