To evaluate the effect of tildacerfont in reducing testicular adrenal rest tumor(s) (TART[s]) in male classic CAH subjects with TART(s) at baseline after 12 weeks on treatment	3.3.	Change in the lesion volume of TART(s) from baseline after 12 weeks on double-blind, placebo-controlled treatment (Week 18) for each treatment group
To characterize dose-exposure of Tildacerfont in CAH	3.4.	Correlation of Tildacerfont plasma concentration vs dose
To evaluate the effect of tildacerfont on biomarkers relative to each other in subjects with classic CAH over 12 weeks	3.5.	Estimate the within subject correlation of A4 and 17-OHP log scale values over time
To evaluate the effect of tildacerfont in improving quality of life (QoL) in subjects with classic CAH after 12 weeks on treatment	3.6.	Change from baseline in SF-36 total score after 12 weeks on double-blind, placebo-controlled treatment (Week 18) for each treatment group

Objective	Efficacy Analysis	
To evaluate the effect of tildacerfont in improving QoL in subjects with classic CAH	3.7.	Change from baseline at Week 76 in SF-36 total score across all ITT subjects
To evaluate the effect of tildacerfont in improving acne in classic CAH subjects with acne at baseline	3.8.	Change from baseline at Week 76 in IGA of acne severity score across all ITT subjects with acne at baseline
To evaluate the effect of tildacerfont in improving hirsutism in female classic CAH subjects with hirsutism at baseline	3.9.	Change from baseline at Week 76 in modified Ferriman Gallwey (mFG) score for hirsutism across all female ITT subjects with hirsutism at baseline
To evaluate the proportion of subjects who can reduce GC use in subjects with classic CAH	3.10.	Proportion of subjects with at least a 5 mg/day hydrocortisone equivalent (HCe) reduction from baseline in GC dose and A4 $\leq$ ULN at Week 76
To evaluate the effect of tildacerfont in reducing TART(s) in male classic CAH subjects with TART(s) at baseline	3.11.	Change in the total lesion volume of TART(s) from baseline at Week 76 across all male ITT subjects with TART(s) at baseline
To evaluate the effect of tildacerfont in reducing A4 in subjects with classic CAH over 12 weeks	3.12.	Assessment of dose response for change from baseline in log ATCH after 12 weeks on double-blind, placebo-controlled treatment (Week 18)

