### 9.3.10 Baseline Values

Baseline values of serum biomarkers (i.e., A4, 17-OHP, and ACTH) are defined as the average of the Day 1, Week 4 and Week 6 assessments that are on or prior to the date of the first dose of double-blind study drug during Part A, allowing for unscheduled assessments to be windowed and replace missed scheduled visits. Visit windowing conventions will be used to identify the assessments that are used to construct baselines (see [Section 9.4](#)). Day 1 values are defined as the last non-missing assessment up to Day 14 for hormone assessments. For all other parameters, baseline values are defined as the last non-missing assessment prior to the first dose of randomized, double-blind study drug in Part A of the study. The following [Table 3](#) provides a guide for the baselines to use in analysis.

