### **10.2.3 Handling of Laboratory Data**

A retest value will be used if the first test is invalidated, e.g., specimen hemolyzed. For non-PK laboratory values that are continuous in nature but are presented as either above or below the respective quantitation limits, the following imputations will be made for the purposes of summarization:

- If value is listed as  $< X$ , then the imputed value will be  $X/2$
- If a value is listed as  $\leq X$ , then the imputed value will be  $X$
- If value is listed as  $> X$ , then the imputed value will be  $X+1$
- If a value is listed as  $\geq X$ , then the imputed value will be  $X$

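### SAP 13.5.4 plans a geometric mean change from baseline in tildacerfont concentration, which cannot be calculated from a drug-free baseline, and sets no slope or correlation for an endpoint named a correlation

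*SAP*

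**What the plan says.** SAP Table 1 names Analysis 3.4 "Correlation of Tildacerfont plasma concentration vs dose". Protocol 9.4.4.2 says that this "will be explored by presentation of PK descriptive statistics by dose and scheduled time point", the time points being Weeks 10 and 18. It mentions no change from baseline. SAP 13.5.4 repeats that plan and adds: "Geometric means and geometric mean change from baseline, along with the associated log scale SDs, will be presented".

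The other provisions that bear on this are:

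- **Baseline.** SAP 9.3.10 gives the three efficacy hormones an averaged baseline. Everything else, PK included, falls under a general rule: "baseline values are defined as the last non-missing assessment prior to the first dose of randomized, double-blind study drug in Part A".
- **Prior treatment.** SAP 5.2.1: "During the Run-in Period, subjects will take placebo for 6 weeks".
- **Change on the log scale.** SAP 9.3.13 and 9.3.14 define it as the log of the post-baseline value over the baseline value, and build the geometric mean ratio from it.
- **Values below quantitation.** SAP 10.2.3 substitutes X/2 for a result reported as below X, but opens with the limit "For non-PK laboratory values that are continuous in nature but are presented as either above or below the respective quantitation limits".
- **Scope.** SAP Section 4 sends the analysis of PK concentration data to a separate SAP. SAP 13.1 nevertheless places Analyses 3.1 to 3.6 in the Week 18 analysis under this plan.

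**The concern.** A change from baseline on the log scale needs a positive baseline. Tildacerfont concentration before any tildacerfont has been given should be zero or below quantitation, so the programmer will meet cells that cannot be filled. With no PK rule in this SAP, a substitution might be chosen after unblinding, and the resulting fold change would reflect the assay's sensitivity rather than the drug.

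The second part is a mismatch between name and output. The endpoint is labelled a correlation, and its objective is to characterise dose-exposure, but this SAP gives no estimator for it. Elsewhere the SAP does give one: Analysis 3.5 extracts a correlation coefficient, and Analysis 3.15 fits a mixed model. That model relates hormone change to concentration, not concentration to dose.

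**Working it through.** The plan states no figure for this endpoint, so there is none to reproduce. The check is whether the statistic exists, what substitution would do to it, and whether the proposed slope can be estimated.

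**1. Is the baseline sample drug-free?**
- By definition, yes: SAP 9.3.10 takes the last value before the first randomised dose.
- By timing, yes: PK is marked at Week 6 in the schedule and drawn at 8 AM ± 1 hour (Protocol 8.4), while study drug is taken between 6 PM and midnight (Protocol 6.1.2).
- Carry-over from any earlier exposure is negligible. The half-life is about 60 hours (Protocol 4.3), so five half-lives are 5 × 60 / 24 = 12.5 days. The run-in lasts 42 days, or 42 × 24 / 60 = 16.8 half-lives.

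**2. Apply SAP 9.3.13.** log(C) − log(0) is infinite for every subject with measurable drug. The geometric mean change therefore does not exist in any active arm.

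**3. Substitute half the lower limit of quantitation (LLOQ), contrary to the limit in SAP 10.2.3.** The ratio becomes C / (LLOQ/2) = 2C / LLOQ. The documents give neither LLOQ nor concentrations. For an assumed geometric mean of 100 units:
- LLOQ 0.1: ratio 2,000
- LLOQ 1: ratio 200
- LLOQ 10: ratio 20

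Subtracting a constant leaves the log-scale SD unchanged, so the statistic adds nothing to the geometric mean.

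**4. The placebo column.** SAP Section 9 asks for a placebo column in Part A summaries by treatment. The PK set (SAP 8.6) does not exclude placebo subjects, because they receive tildacerfont from Part B. Their Week 10 and 18 values are expected to be drug-free, so even the plain geometric mean cannot be calculated in that column without a rule for values below quantitation.

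**5. Can a slope be estimated?** Model at one visit: log(C) = a + b·log(dose), at 50, 100 and 200 mg.
- Variance of log dose with equal arms = (2/3)(ln 2)² = 0.320.
- SE(b) = SD / √(n × 0.320).
- Between-subject log SD is assumed at 0.3, 0.5 and 0.8, since the documents give none.

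| Active subjects | SE(b) | t(0.95) | 90% CI half-width |
|---|---|---|---|
| 54 (3 × 18) | 0.072, 0.120, 0.192 | 1.675 (52 df) | 0.12, 0.20, 0.32 |
| 45 (3 × 15) | 0.079, 0.132, 0.211 | 1.681 (43 df) | 0.13, 0.22, 0.35 |

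The 54 and 45 are the plan's targets before and after its assumed 15% dropout (Protocol 9.2).

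**The case against.** The best reply is that only one of several listed statistics is defective. SAP 13.5.4 also plans PK descriptive statistics, geometric means and log-scale SDs by dose at Weeks 10 and 18, and none of these needs a baseline in the active arms. The stray phrase closely matches SAP 13.3.4 and 13.5.3.2, where a change from baseline makes sense, so it may simply be carried-over text. That is an inference, but a reasonable one.

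The planned table also holds most of what a slope needs. Because the doses are equally spaced on the log scale, the least-squares slope with balanced arms is ln(GM200/GM50) / ln 4, where GM is the geometric mean at that dose, and its SE follows from the tabulated SDs and numbers. Both documents state the descriptive method and agree on it.

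Finally, SAP Section 4 assigns PK concentration analysis to another plan without qualification. The non-PK limit in SAP 10.2.3 is consistent with PK rules sitting there.

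All of this stands, and it keeps the point small. It does not make the change from baseline calculable here, and it does not give the placebo column a rule. SAP 13.1 keeps Analysis 3.4 in this plan, so the text of 13.5.4 needs either correction or a cross-reference.

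**Conclusion.** One statistic in SAP 13.5.4, the geometric mean change from baseline in concentration, cannot be calculated under this SAP. An endpoint named a correlation also has no slope or correlation specified in it. The first conclusion rests on definitions and timing in the documents. The second is limited to this SAP.

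A reader might infer that Analysis 3.4 yields nothing usable, or that the dose-concentration relationship is never estimated. The documents do not support that: the geometric means by dose are sound, and a PK SAP that was not supplied may contain both a rule for values below quantitation and a dose-exposure model. Nor does the defect undermine the exposure-response aim in Protocol 4.2 and 4.3, which concerns hormone response to concentration and has its own model in Analysis 3.15.

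Severity is minor. The endpoint is exploratory, SAP 10.5 gives it no alpha, and no primary or secondary result depends on it. The LLOQ values, the concentration of 100 and the log SDs are assumptions. The precision figures also assume equal arms and a measurable sample from each active subject counted.

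**What to change.** In SAP 13.5.4:

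- Delete the change from baseline for PK. Keep geometric means and log-scale SDs for the active arms at Weeks 10 and 18.
- Use the Week 6 sample only to confirm absence of drug. Count and list values below quantitation by arm, placebo included.
- Add the slope of log(concentration) on log(randomised dose) in the active arms at Weeks 10 and 18, with its confidence interval and a stated level (90% in the figures above). If the PK SAP already holds this model, cross-refer to it instead.
- Describe the slope as the dose relationship of a single morning concentration. An 8 AM ± 1 hour sample after dosing between 6 PM and midnight falls about 7 to 15 hours after the dose, so it does not measure total exposure.

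The cost is a few lines of SAP text and at most one short model, using samples already scheduled. It should be settled before the Week 18 unblinding.
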